8.5.4. Second Course Phase (Retreatment Period)

Subjects who stop pembrolizumab with SD or better may be eligible for up to 18 cycles of additional pembrolizumab therapy if they progress after stopping study treatment. This retreatment is termed the Second Course Phase of this study and is only available if the study remains open and the subject meets the following conditions:

Either

- Stopped initial treatment with pembrolizumab after attaining an investigatordetermined confirmed CR according to RECIST 1.1, and
- Was treated for at least 24 weeks with pembrolizumab before discontinuing therapy
- Received at least two treatments with pembrolizumab beyond the date when the initial CR was declared

OR

• Had SD, PR or CR and stopped pembrolizumab treatment after 35 cycles of study therapy for reasons other than disease progression or intolerability

AND

- Experienced an investigator-determined confirmed radiographic disease progression after stopping their initial treatment with pembrolizumab
- Did not receive any anti-cancer treatment since the last dose of pembrolizumab
- Has a performance status of 0 or 1 on the ECOG Performance Scale
- Demonstrates adequate organ function as detailed in Section 6.1
- Female subject of childbearing potential should have a negative serum pregnancy test within 72 hours prior to receiving retreatment with study medication.
- Female subject of childbearing potential should be willing to use 2 methods of birth control or be surgically sterile, or abstain from heterosexual activity for the course of the study through 120 days after the last dose of study medication (Section 6.5.2). Subjects of child bearing potential are those who have not been surgically sterilized or have been free from menses for > 1 year.
- Male subject should agree to use an adequate method of contraception starting with the first dose of study therapy through 120 days after the last dose of study therapy.
- Does not have a history or current evidence of any condition, therapy, or laboratory abnormality that might interfere with the subject's participation for the full duration of the trial or is not in the best interest of the subject to participate, in the opinion of the treating investigator.

Subjects who restart treatment will be retreated at the same dose and dose interval as when they last received pembrolizumab. Treatment will be administered for up to 18 additional cycles.

Visit requirements are outlined in Section 10.0 – study calendar.

8.5.5. Treatment Beyond Disease Progression

See section 6.8 for further details. The decision to continue study treatment after the 1st evidence of disease progression is at the Investigator's discretion based on the clinical status of the subject as described in table 5. Confirmatory imaging maybe performed as early as 28 days later; alternatively, the scan performed at the next scheduled time point (every 42 days \pm 7 days) may be used as confirmation. Subjects may receive study treatment while waiting for confirmation of PD if they are clinically stable as defined by the following criteria:

- Absence of signs and symptoms (including worsening of laboratory values) indicating
- disease progression
- No decline in ECOG performance status
- Absence of rapid progression of disease
- Absence of progressive tumor at critical anatomical sites (e.g., cord compression)
- Requiring urgent alternative medical intervention
- Subjects exhibiting toxicity from trial therapy requiring discontinuation of trial therapy as outlined in Section 6.4.and 7.0 may NOT continue to receive trial therapy.

	Clinically stable		Clinically unstable				
	Imaging	Treatment	Imaging	Treatment			
1 st radiologic evidence of PD	Repeat imaging at > 4 weeks at site to confirm PD	May continue study treatment at the Investigator's discretion while awaiting confirmatory scan by site	Repeat imaging at > 4 weeks to confirm PD per physician discretion only	Discontinue treatment			
Repeat scan confirms PD (no reduction in tumor burden from prior scan)	No additional imaging required	Discontinue treatment	No additional imaging required	NA			
Repeat scan confirms PD (reduction in tumor burden from prior scan)	Continue regularly scheduled imaging assessments	Continue study treatment after consultation with Sponsor Investigator	Continue regularly scheduled imaging assessments	May restart study treatment if condition has improved and/or clinically stable per Investigator and Sponsor Investigators's discretion			
Repeat scan shows SD, PR or CR	Continue regularly scheduled imaging assessments	Continue study treatment at the Investigator's discretion	Continue regularly scheduled imaging assessments	May restart study treatment if condition has improved and/or clinically stable per Investigator's discretion			

Table 5

NOTE: If a subject with confirmed radiographic progression (i.e. 2 scans at least 28 days apart demonstrating progressive disease) is clinically stable or clinically improved, and there is no further increase in the tumor dimensions at the confirmatory scan (as assessed by the investigator/site radiologist), an exception may be considered to continue treatment upon consultation with the Sponsor Investigator. All decisions to treat beyond progression

must be approved by the PI and the rationale must be clearly documented within the study records.

Upon radiographic or clinical evidence of second progression, defined as an additional 20% or greater increase in total sum of tumor burden, patients must discontinue study therapy

9.0 Adverse Events

9.1. Definitions:

9.1.1. Adverse Events

An adverse event is defined as any untoward medical occurrence in a patient or clinical investigation subject administered a pharmaceutical product and which does not necessarily have to have a causal relationship with this treatment. An adverse event can therefore be any unfavorable and unintended sign (including an abnormal laboratory finding, for example), symptom, or disease temporally associated with the use of a medicinal product or protocol-specified procedure, whether or not considered related to the medicinal product or protocol-specified procedure.

Any worsening (i.e., any clinically significant adverse change in frequency and/or intensity) of a preexisting condition that is temporally associated with the use of the pembrolizumab is also an adverse event.

Changes resulting from normal growth and development that do not vary significantly in frequency or severity from expected levels are not to be considered adverse events. Examples of this may include, but are not limited to, teething, typical crying in infants and children and onset of menses or menopause occurring at a physiologically appropriate time.

9.1.2. Serious Adverse Events

Serious Adverse Event (SAE) is an AE that is fatal or life threatening, requires inpatient hospitalization or prolongation of existing hospitalization (for > 24 hours), persistent or significant incapacity or substantial disruption of the ability to conduct normal life functions, or is a congenital anomaly/ birth defect, or results in any important medical event that may not result in death, be life threatening, or require hospitalization may be considered an SAE when, based upon appropriate medical judgment, may jeopardize the subject and may require medical or surgical intervention to prevent any of the above outcomes. A "life-threatening" adverse event places the patient at immediate risk of death in the judgment of the investigator or sponsor.

Note: In addition to the above criteria, adverse events meeting either of the below criteria, although not serious per ICH definition, are considered serious for the purpose of this study and therefore must be reported in the same timeframe as SAEs.

- Is a new cancer (that is not a condition of the study);
- Is associated with an overdose.

9.1.3. Definition of Overdose for This Protocol

For purposes of this trial, an overdose of pembrolizumab will be defined as any dose of 1,000 mg or greater (\geq 5 times the indicated dose). No specific information is available on the treatment of overdose of pembrolizumab. Appropriate supportive treatment should be provided if clinically indicated. In the event of overdose, the subject should be observed closely for signs of toxicity. Appropriate supportive treatment should be provided if clinically indicated.

9.1.4. Severity Rating

The investigator will evaluate the severity of each adverse event. NCI Common Terminology Criteria for Adverse Events (CTCAE v.4.0) or study specific toxicity tables provided in the protocol define severity. If not included in CTCAE v.4.0, severity is expressed in numerical grade using the following definitions:

- 1. Grade 1: Mild-asymptomatic or mild symptoms; clinical or diagnostic observations only; intervention not indicated.
- 2. Grade 2: Moderate-minimal, local or noninvasive intervention indicated; limiting age appropriate instrumental ADL.
- 3. Grade 3: Severe-severe or medically significant but not immediately lifethreatening; hospitalization or prolongation of hospitalization indicated; disabling; limiting self care ADL.
- 4. Grade 4: Life-threatening consequences; urgent intervention indicated.
- 5. Grade 5: Death related to AE

9.1.4.1. Attribution/Relationship to study drug

- 1. Definite clearly related
- 2. Probable likely related
- 3. Possible may be related
- 4. Unlikely doubtfully related
- 5. Unrelated clearly not related

9.1.5. Expectedness

An Expected Adverse Event is one where the specificity or severity is consistent with the current information available from the resources.

An Unexpected Adverse Event is one where the nature, severity, or frequency of the event is related to participation in the research is not consistent with either:

1. The known or foreseeable risk of adverse events associated with the procedures involved in the research that are described in (a) the protocol-related documents, such as the IRB-approved research protocol, any applicable investigator brochure, and the current IRB-approved informed consent document, and (b) other relevant sources of information, such as product labeling and package inserts: or

2. The expected natural progression of any underlying disease, disorder, or condition of the subject (s) experiencing the adverse event and the subjects(s) predisposing risk factor profile for the adverse event.

(OHRP Guidance on reviewing unanticipated problems 2007)

9.1.6. Events of Clinical Interest

Selected non-serious and serious adverse events are also known as Events of Clinical Interest (ECI).

Events of clinical interest for this trial include:

- 1. An overdose of Merck product that is not associated with clinical symptoms or abnormal laboratory results.
- 2. an elevated AST or ALT lab value that is greater than or equal to 3X the upper limit of normal and an elevated total bilirubin lab value that is greater than or equal to 2X the upper limit of normal and, at the same time, an alkaline phosphatase lab value that is less than 2X the upper limit of normal, as determined by way of protocol-specified laboratory testing or unscheduled laboratory testing.*
- *Note: These criteria are based upon available regulatory guidance documents. The purpose of the criteria is to specify a threshold of abnormal hepatic tests that may require an additional evaluation for an underlying etiology.

9.2. Assessing, Recording and Reporting Adverse Events

9.2.1. Investigative site recording responsibilities:

- 1. Upon identification of an AE or SAE, the site investigator will utilize the above definitions to properly classify the event. Each category listed above; in section 9.1; must be recorded for each event. Adverse events will be recorded from the time of treatment initiation through 120 days following cessation of treatment.
- 2. All AEs and SAEs will be recorded in the "AE case report forms" (CRF) and in progress reports with details about the grade and attribution of each episode, action taken with respect to the study drug, and the patient's outcome will be recorded in the CRF. All events will be recorded on case report forms for the duration of the study until they resolve.
- 3. All SAEs will be recorded on the FDA MedWatch form 3500a. After submitting the initial report it may be necessary to submit follow up reports to the Sponsor, Merck and the FDA should the event require further investigation.

9.2.2. Investigative site reporting responsibilities:

1. The investigator/ site is responsible to report all SAEs that occur on or after the first day of study treatment to the IST Regulatory Specialist within 24 hours of becoming aware

of the event.

Each investigator is responsible to report all SAEs to their local IRB following guidelines set by that IRB. The FCCC OCR reserves the right to request an event be reported to the IRB at their discretion. Copies of events reviewed by the IRB must be sent email to [contact].

- If the investigator or IRB feels the event warrants a revision to the informed consent that was not already initiated by the OCR, draft revisions will be made in track changes and submitted to the OCR for consideration. Any consent revisions must receive OCR approval prior to submission to the IRB.
- 3. Any investigator who is in doubt of whether a particular AE needs to be reported is directed to call the Study Monitor for confirmation with the Sponsor Investigator.
- 4. If the results of an investigator or OCR investigation show an adverse event not initially determined to be reportable is so reportable, the investigator will report the event following the above guidelines based on the date the determination is made.
- 5. Copies of all related correspondence and reporting documents must be submitted to the ISRU and will be maintained in the trial master file.

Participating sites should report events to:

Investigator-Sponsored Research Unit Office of Clinical Research Fox Chase Cancer Center [contact]

9.2.3. Additional reporting guidelines for investigative sites:

Following events must be reported by investigative sites to IST Regulatory Specialist within 24 hours of being aware of the event:

• Serious Adverse Events

For the time period beginning at treatment initiation through 120 days following cessation of treatment, or 30 days following cessation of treatment if the subject initiates new anticancer therapy, whichever is earlier, any serious adverse event, or follow up to a serious adverse event, including death due to any cause other than progression of the cancer under study whether or not related to the pembrolizumab must be reported.

• Overdose

If an adverse event(s) is associated with ("results from") the overdose of a pembrolizumab, the adverse event(s) is reported as a serious adverse event, even if no other seriousness criteria are met.

If a dose of pembrolizumab meeting the protocol definition of overdose is taken without any associated clinical symptoms or abnormal laboratory results, the overdose is reported as a non-serious Event of Clinical Interest (ECI), using the terminology "accidental or intentional overdose without adverse effect."

• New cancer Incident

If a new type of cancer is detected, which is not a condition of the study, it should be reported as a serious adverse event.

• Pregnancies and Lactations

Pregnancies and lactations that occur from the time of treatment initiation through 120 days following cessation of pembrolizumab, or 30 days following cessation of treatment if the subject initiates new anticancer therapy, whichever is earlier, must be reported .

All reported pregnancies must be followed to the completion/termination of the pregnancy. Pregnancy outcomes of spontaneous abortion, missed abortion, benign hydatidiform mole, blighted ovum, fetal death, intrauterine death, miscarriage and stillbirth must be reported as serious events (Important Medical Events). If the pregnancy continues to term, the outcome (health of infant) must also be reported.

• Events of Clinical Interest (ECIs)

For the time period beginning at treatment initiation through 120 days following cessation of treatment, or 30 days following cessation of treatment if the subject initiates new anticancer therapy, whichever is earlier, any ECI, or follow up to an ECI, whether or not related to pembrolizumab must be reported.

9.2.4. Sponsor Reporting Responsibilities:

- 1. Adverse events which meet all of the following criteria must be reported to all participating institutions for IRB submission within 2 weeks of notification of the event:
 - i. Unexpected (in terms of nature, severity, or frequency) given (a) the research procedures that are described in the protocol-related documents, such as the IRB-approved research protocol and informed consent document; and (b) the characteristics of the subject population being studied;
 - ii. Possibly related to participation in the research (possibly related means there is a reasonable possibility that the incident, experience, or outcome may have been caused by the procedures involved in the research); and

- iii.Serious (refer to above definition) or otherwise one that suggests that the research places subjects or others at a greater risk of physical or psychological harm than was previously known or recognized.
- 2. Copies of all related correspondence and reporting documents will be maintained in a centralized regulatory file for this study at OCR.
- 3. SAEs that are related, unexpected, fatal, or life-threatening are reportable through the Food and Drug Administration (FDA) MedWatch program by telephone or fax no later than 7 calendar days after initial receipt of the information. Further information on the timing of submissions are as directed by FDA guidelines.(http://www.fda.gov/medwatch/index.html). Serious, unexpected events that suggest significant clinical risk will be submitted to within 15 calendar days after initial receipt of this information.

Food and Drug Administration: Central Document Room Center for Drug Evaluation and Research Food and Drug Administration [name] [name] 20705

[contact] for any further questions regarding where to send drug mandatory reporting forms

9.2.5. Sponsor Reporting Responsibilities to Merck:

Sponsor must report the following to Merck Global Safety within 2 working days of notification by investigative sites:

- Serious Adverse Events
- All reports of overdose with and without an adverse event
- Pregnancy and Lactation
- Events of Clinical Interest (ECIs)

SAE reports and any other relevant safety information are to be forwarded to the Merck Global Safety (Attn: Worldwide Product Safety; [contact])

A copy of all 15 Day Reports and Annual Progress Reports is submitted as required by FDA, Investigators will cross reference this submission according to local regulations to the Merck Investigational Compound Number (IND, CSA, etc.) at the time of submission. Additionally investigators will submit a copy of these reports to Merck & Co., Inc. (Attn: Worldwide Product Safety; [contact]) at the time of submission to FDA.

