5.5. Patient Registration

Participants may be registered from 8:00 am to 4:00 pm EST excluding holidays by emailing the study monitor at: [contact]. Eligible participants will be entered on study centrally once the following items have been received by email:

- Completed registration form
- Consent and HIPAA signature pages
- Eligibility checklist

Following registration, participants must begin protocol treatment within 7 days of registration. Issues that would cause treatment delays must be discussed with the Principal

Copyright© 2016 Fox Chase Cancer Center[®] Clinical Trials Operations. All rights reserved.

Version Date 03/03/17

Investigator. If a registered participant does not receive protocol therapy following registration, the participant will be recorded as withdrawn from study. The Study Monitor must be notified as soon as possible if a participant does not begin protocol treatment as scheduled. For additional registration questions, please email [contact] or call [contact].

The study monitor or their designee will notify the site by email once registration is confirmed and the sequence number has been assigned. Participants must be registered and have received a sequence number prior to the initiation of treatment.

Exceptions to the current registration policies will not be permitted.

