8.3.1. Biomarker Evaluations

Blood Collection for correlative studies/biomarkers

Sample collection, processing, storage, and shipment instructions for samples is provided in the Appendix (section 17.2).

Tumor tissue collection for correlative studies

Pathology samples from archived tumor biopsies (or optional fresh biopsy done before treatment initiation, if no archived tissue available) are to be submitted within 28 days of starting cycle 1. Representative FFPE tumor tissue blocks specimen are to be submitted to the Fox Chase Cancer Center PSL.

The following pathology material needs to be submitted:

- Paraffin embedded biopsy or cell block, and
- Any available pathology report related to that tumor sample

NOTE: If a block is unavailable for submission, slides are to be submitted. All slides must be adequately labeled, with slides numbered sequentially in the order cut. Alternative submission requirement:

- One (1) H&E slide, and
- Ten (10) 4 µm unstained air-dried on plus slides.

Shipment of pathology samples is outlined in the Appendix (section 17.2)

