^a Total of 35 treatment cycles. Treatment cy ^b Patients should be assessed every 9 weeks every 12 weeks (± 7 days). Once a subject ex ^c Check during treatment phase every 3 cycl ^d Preferably a contrast-enhanced CT scan of with contrast). Subsequent imaging should be treatment for the first year; subsequent ima ^e Imaging studies will be done every 9 weeks the treatment phase.	(63 ± 7 days) for the periences confirmed es (screening, cycle 3, chest/abdomen and p be of the same modal ging will be every 12	first 1 y disease 6, 9, 12 pelvis (If ity as th weeks (e progre 2, 15, 18 f cannot ie imagi ± 7days	ssion oi 3, etc.) 1 receive ng at ba) therea	e contrast, can s aseline. Imaging after during the	nti-cancer thera substitute for CT s studies will be treatment phas	py they move chest withou done every 9 v	into survival fo t contrast and weeks (± 7 days	llow-up MRI abdomer s) after initiati	n/pelvis ing	

Trial Period:	Screening Phase	Treatment Cycles ^a			End of Treatment ^m		Pos	Post-Treatment		
Treatment Cycle/Title:	Study Screening	1	2	3	Cycle 4 and beyond	35 cycles completed OR	Safety Follow-up	Safety Follow-up	Follow Up Visits ^b	Survival Follow- Up
Scheduling Window (Days):	-28 to -1		± 3	± 3	± 3	At time of Discon	30 days post discon	120 days post discon		Every 12 weeks

^f Peripheral blood samples will be collected immediately prior to cycle 1, immediately prior to dose 1 (time 1), prior to dose 3, cycle 3 day 1 (time 2) and at time of progression (time 3). For sampling, handling, processing, and shipping, please see Appendix (Section 17.2)

^g Within 10 days of treatment initiation

^h Within 72 hours of treatment initiation if participant is a woman of child bearing potential

Vital signs consist of temperature, pulse, respiration, and blood pressure and will be monitored every 15 minutes during the infusion and at 60 minutes after completion of each infusion.

^j A direct bilirubin must be performed if the total bilirubin is above the upper limit of normal. This will also include Lipase testing.

^k If archival tissue is not available, patient may undergo an optional fresh biopsy of tumor before day 1 of therapy. All archived tissues must be received within 28 days of starting cycle 1.

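### Complications of the optional pre-treatment biopsy that begin before first dose fit the adverse event definition, but nothing requires sites to record them as adverse events or report them within 24 hours

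*Combined protocol and SAP*

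**What the plan says.** **Definition.** Section 9.1.1 opens with a patient or "clinical investigation subject administered a pharmaceutical product". Its next sentence widens the scope to any unfavorable sign, symptom or disease "temporally associated with the use of a medicinal product or protocol-specified procedure".

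**Biopsy.** Section 8.3.1, under tissue collection for correlative studies, allows an "optional fresh biopsy done before treatment initiation, if no archived tissue available". Footnote k of the calendar in 10.1 says the "patient may undergo an optional fresh biopsy of tumor before day 1 of therapy". Section 4.7 places it at enrollment.

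**Recording.** Section 9.2.1 states: "Adverse events will be recorded from the time of treatment initiation through 120 days following cessation of treatment".

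**Reporting.** Section 9.2.2 makes the site "report all SAEs that occur on or after the first day of study treatment" to the coordinating centre's regulatory specialist, with a 24-hour limit. Section 9.2.3 sets the same limit "For the time period beginning at treatment initiation through 120 days following cessation of treatment", with an earlier end date if new anticancer therapy begins.

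**Patients who do not start.** Section 5.5 says: "If a registered participant does not receive protocol therapy following registration, the participant will be recorded as withdrawn from study". It also requires prompt notice to the Study Monitor.

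**The concern.** The plan treats harm from research procedures as its business. Besides 9.1.1, section 9.1.5 judges expectedness against the known risks of the research procedures. Section 9.2.4 obliges the sponsor to alert all participating institutions to serious, unexpected events that those procedures may have caused. Yet the collection rules open only after the one invasive procedure done for research has taken place. The biopsy serves immunohistochemistry and sequencing and is not an entry requirement, so its risk is research risk.

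What is at stake is oversight of that procedure. The sponsor's duties in 9.2.4 and 9.2.5 run from notification. If a site need not notify a bleed or pneumothorax that occurs before dosing, those duties may never be triggered, and the sponsor may lack the information to judge whether the biopsy should continue.

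**Working it through.** The plan gives no figure to reproduce, so the check sets the rules side by side along a patient's timeline.

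**1. When each rule starts**

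| Place in the protocol | What it governs | Start |
|---|---|---|
| 9.2.1 | AE recording on the CRF | Treatment initiation |
| 9.2.2 | 24-hour SAE report | First day of study treatment |
| 9.2.3 | 24-hour report of SAEs and events of clinical interest | Treatment initiation |
| 10.1, Review Adverse Events row | Scheduled AE review | Cycle 1; Screening cell empty |
| 12.1 and 13.4.1 | Evaluable for AEs or toxicity | First pembrolizumab treatment |
| 4.7, 8.3.1, 10.1 footnote k | Optional biopsy | Before day 1 |

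The order is consent, screening (days -28 to -1) with any biopsy, first dose, and only then the AE and SAE windows.

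**2. Where a biopsy complication falls**

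- *Begins and resolves before first dose:* outside 9.2.1, 9.2.2 and 9.2.3.
- *Begins before first dose and is still active at baseline:* can enter medical history under 8.1.3, without the grade and attribution required of an AE. Section 9.1.1 would pick up a later worsening only if it were associated with pembrolizumab.
- *Begins on or after first dose:* inside the window.
- *Begins before first dose in a patient who is never dosed:* no window ever opens.

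The gap is therefore defined by onset before first dose. Its length is the time from biopsy to first dose. The 28-day screening period is an upper limit on that time, not its usual value.

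**3. Size**

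The documents do not say how many patients lack archived tissue or would accept a biopsy. For scale only, assume that 10% to 30% of the 21 planned patients are biopsied: 0.10 × 21 = 2.1 and 0.30 × 21 = 6.3, or about 2 to 6 patients. Assume further that 1% to 5% of biopsies cause a serious complication: 2.1 × 0.01 = 0.021 and 6.3 × 0.05 = 0.315, or about 0.02 to 0.3 serious events in the whole trial. Neither range comes from the documents.

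**4. Effect on the analyses**

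Under 13.1, the stopping rule counts treatment discontinuations due to treatment-related events, and the safety analysis includes patients who received at least one dose. Neither uses pre-dose events, and nor does the objective response rate.

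**The case against.** A reader might infer that biopsy complications are never captured anywhere, or that a patient whose complication prevents dosing leaves the trial unnoticed. The documents do not support either reading:

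- Section 9.2.2 also requires all SAEs to go to the local IRB, with no start date, and copies of IRB-reviewed events to be forwarded.
- Section 14.1 has SAEs reviewed in real time by the site, the coordinating unit and the Sponsor Investigator, again with no start date. The unit also monitors each accrued participant's records.
- Section 9.2.2 sends doubtful cases to the Study Monitor.
- Section 8.5.3 asks for all AEs before the 120-day safety visit to be recorded and gives no start.
- Section 5.5 ensures that the coordinating centre hears when a registered patient does not begin treatment.
- The local IRB guidelines and the separate Data and Safety Monitoring Plan are not among the documents and may cover more.

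The definition is also less clear-cut than its procedure limb suggests. Because 9.1.1 opens with a subject already given a product, one fair reading is that a pre-dose event is not yet an AE. The procedure limb would still apply to blood draws and imaging after dosing. The start at first dose is consistent across sections and may be deliberate.

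These points rule out the broad claim but do not close the gap. The IRB route depends on each board's guidelines and brings no CRF entry or 24-hour limit. Section 14.1 reviews SAEs that have reached the reviewers; it does not require a site to send a pre-dose one. The explicit cut-off in 9.2.2 leaves a site little reason for doubt. The sentence in 8.5.3 concerns the end of follow-up, whereas 9.2.1 states the start. The notice in 5.5 reports that treatment did not begin, need not describe an adverse event, and applies only after registration, which an earlier screening biopsy may precede. As for the definition, 9.1.5 and 9.2.4 also refer to research procedures, so the text is at least ambiguous and should be aligned.

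**Conclusion.** The point holds in a limited form. For biopsy complications with onset before first dose, 9.2.1 to 9.2.3 and the calendar require neither an AE record nor a 24-hour SAE report to the coordinating centre. Other routes may bring some of these events to light, but only partly and indirectly.

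This rests on reading the procedure limb of 9.1.1 as covering patients not yet dosed, which 9.1.5 and 9.2.4 support but the opening words of 9.1.1 do not settle.

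The practical size is probably small. The biopsy is optional and confined to patients without archived tissue, and 5.2.1 requires histologic or cytologic confirmation, so many patients are likely to have stored material. The documents give no count, and the ranges in the working are assumptions. Neither the efficacy conclusion nor the toxicity stopping rule changes. This is a worthwhile, inexpensive correction to safety oversight, not a flaw in the trial's inference.

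**What to change.** In 9.2.1, 9.2.2 and 9.2.3, state that AEs attributed to a protocol-specified procedure are recorded, and that such SAEs are reported within 24 hours, from informed consent, including in patients who never receive pembrolizumab. Mark the Screening cell of the Review Adverse Events row in 10.1, with a footnote limiting it to these events. State that the pembrolizumab toxicity analysis and the stopping rule in 13.1 are still counted from first dose.

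Section 8.5.1 already places written consent before any study procedure, so the new start point exists. The cost is a sentence in three subsections, one calendar cell with its footnote, and a few extra CRF entries, mainly for biopsied patients. No visit or test is added. Because only procedure-attributed events are covered, sites need not collect unrelated events during screening.
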